6.12.3 Primary Analysis

The number and percent of patients with valid diaries will be tabulated by treatment group and visit and a listing of diary completion will be provided. Descriptive statistics for the actual values by visit (including baseline) and change from baseline to each post-baseline visit (Visits 3, 4 and 5/EOT) in average daily ON-time without troublesome dyskinesia (hours) will be presented.

Change from baseline in average daily ON-time without troublesome dyskinesia (hours) will be analysed using a mixed model for repeated measures (MMRM) for all patients in the FAS. Change from baseline to Week 12 is the timepoint of interest for this analysis. Any missing data is assumed to be missing at random (MAR) for this analysis.

The model will include randomized treatment (2.5 mg, 5.0 mg, 7.5 mg, or placebo b.i.d.), visit, country, and treatment by visit interaction as explanatory, fixed effect variables. Country will be

Worldwide Clinical Trials Controlled Quality Management Document		
WORLDWIDE CLINICAL TRIALS	Sponsor:	Integrative Research Laboratories Sweden AB
	Protocol Number:	IRL790C005
STATISTICAL ANALYSIS PLAN. PHASE 2-3-4		

weighted by the number of patients participating from each county. Baseline value for average daily hours of ON time without troublesome dyskinesia will be included as a continuous covariate along with the randomisation stratification factor of daily hours spent in ON-time with troublesome dyskinesia (<6 hours, \geq 6 hours).

An unstructured covariance matrix will be assumed for within-patient correlation over time. If the model fails to converge, the first approach for which the model converges among the following will be used: banded Toeplitz (TOEP), compound symmetry (CS) and variance component (VC).

The LS mean estimate, corresponding SE, and 95% CI for the change from baseline at each postbaseline visit will be obtained from the model and presented for each treatment group. The estimated treatment difference for each dose level compared to placebo and the combined dose levels compared to placebo, the corresponding SE, and p-value will also be presented by visit.

A line plot showing the LS mean ($\pm 95\%$ CI) change from baseline at each visit for each treatment group will also be provided.

The following is the sample SAS code that will be used for this analysis:

```
PROC MIXED DATA= analysis (where = (avisitn ne 0));
    ODS OUTPUT LSMeans=LSMeans Diffs=Diffs LSMEstimates=Estimates;

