    CLASS USUBJID STRATF TRT01PN AVISITN COUNTRY;
   MODEL CHG = BASE STRATF TRT01PN AVISITN COUNTRY TRT01PN*AVISITN / DDFM=KR
s;
    REPEATED AVISITN / SUBJECT=USUBJID TYPE=UN;
    LSMEANS TRT01PN*AVISITN / CL DIFF OM;
    LSMESTIMATE TRT01PN*AVISITN 'Difference at Week 4' 1 0 0 1 0 0 1 0 0 -3 0
0 divisor = 3 / CL e OM;
    LSMESTIMATE TRT01PN*AVISITN 'Combined at Week 4' 1 0 0 1 0 0 1 0 0 0 0 0
divisor = 3 / CL e OM;
    LSMESTIMATE TRT01PN*AVISITN 'Placebo at Week 4' 0 0 0 0 0 0 0 0 0 3 0 0
divisor = 3 / CL e OM;
    LSMESTIMATE TRT01PN*AVISITN 'Difference at Week 8' 0 1 0 0 1 0 0 1 0 0 -3
0 divisor = 3 / CL e OM;
    LSMESTIMATE TRT01PN*AVISITN 'Combined at Week 8' 0 1 0 0 1 0 0 1 0 0 0 0
divisor = 3 / CL e OM;
    LSMESTIMATE TRT01PN*AVISITN 'Placebo at Week 8' 0 0 0 0 0 0 0 0 0 0 3 0
divisor = 3 / CL e OM;
    LSMESTIMATE TRT01PN*AVISITN 'Difference at Week 12' 0 0 1 0 0 1 0 0 1 0 0
-3 divisor = 3 / CL e OM;
```

QMD Ref: Worldwide-TMP-ST-005-7.0 Effective: 12Aug2019	Governing QMD: Worldwide-SOP-ST-001	
Confidentiality Statement		
This document is the property of Worldwide Clinical Trials Inc. and may not be duplicated, copied, altered or removed from company without prior approval from Worldwide Quality Assurance or in compliance with Worldwide Standard Operating Procedures.		

REF: Worldwide-TMP-QA-001f-1.3

Worldwide Clinical Trials Controlled Quality Management Document		
WORLDWIDE CLINICAL TRIALS	Sponsor:	Integrative Research Laboratories Sweden AB
	Protocol Number:	IRL790C005
STATISTICAL ANALYSIS PLAN. PHASE 2-3-4		

RUN;

Where USUBJID = Subject Number; TRT01PN = Planned Treatment Group Number; AVISITN = Visit Number; BASE = Baseline Value; CHG = Change from Baseline Value; COUNTRY = Country; STRATF = Stratification Factor.

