imputation model that will be used to impute missing observations in the placebo group. The missing values for each variable will be imputed based on a model simulated from the posterior predictive distribution of the conditional regression model fitted on the imputed variable using only the observations from the placebo group.

This will be implemented by utilizing the MONOTONE REG statement and MNAR statement with option MODEL of SAS' PROC MI with options nimpute = 20 and seed = 32641726.

The following is the sample SAS code that will be used to implement the control-based pattern mixture imputation:

```
PROC MI DATA=DATAIN OUT=DATAIN_MONO SEED=32641726 NIMPUTE=1;
BY TRT01PN;
VAR BASE ONHOURS3-ONHOURS5;
MCMC CHAIN=MULTIPLE IMPUTE=MONOTONE PRIOR = JEFFREYS;
RUN;
PROC MI DATA= DATAIN_MONO SEED=32641726 NIMPUTE=20
OUT=DATA_IMPUTED;
CLASS TRT01PN STRATF;
MONOTONE REG(BASE ONHOURS3-ONHOURS5);
MNAR MODEL(ONHOURS3-ONHOURS5 / MODELOBS=(TRT01P='Placebo'));
VAR STRATF BASE ONHOURS3-ONHOURS5;
RUN;
```

Once the missing diary data has been imputed for all visits, the change from baseline at each visit will be calculated and consequently will be analysed using the same MMRM model employed in the primary analysis for each iteration of the imputed dataset.

Then the results are to be summarized using PROC MIANALYZE, where the treatment group LS means and their differences between treatments will be combined across all 20 imputed datasets:

```
PROC SORT DATA= LSMEANS; BY TRT01PN AVISITN _IMPUTATION_; RUN;
PROC MIANALYZE DATA= LSMEANS;
MODELEFFECTS ESTIMATE;
STDERR STDERR;
ODS OUTPUT PARAMETERESTIMATES= LSMEANS_COMB;
BY TRT01PN AVISITN;
RUN;
```

QMD Ref: Worldwide-TMP-ST-005-7.0 Effective: 12Aug2019	Governing QMD: Worldwide-SOP-ST-001	
Confidentiality	v Statement	
This document is the property of Worldwide Clinical Trials Inc. and may not be duplicated, copied, altered or removed from company without		
prior approval from Worldwide Quality Assurance or in compl	iance with Worldwide Standard Operating Procedures.	

REF: Worldwide-TMP-QA-001f-1.3

PROC SORT DATA= DIFFS; BY TRT01PN; RUN; PROC MIANALYZE DATA= DIFFS(WHERE=(AVISITN=_AVISITN)); MODELEFFECTS ESTIMATE; STDERR STDERR; ODS OUTPUT PARAMETERESTIMATES= DIFFS_COMB; BY TRT01PN AVISITN; RUN;

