6.12.5.2 ANCOVA Analysis

An analysis of covariance (ANCOVA) will also be performed using the FAS. The ANCOVA model will be adjusted for the following covariates: randomized treatment, baseline value for average daily hours of ON time without troublesome dyskinesia (continuous covariate), as well as randomisation stratification factor for daily hours spent in ON-time with troublesome dyskinesia (<6 hours, \geq 6 hours). The dependent variable is the change from baseline in average daily ON-time (hours) at Week 12. Missing observations will not be imputed.

The LS means, SEs, and 95% CIs will be provided for each treatment group, as well as treatment difference estimates, SEs, and p-values for each dose level and combined dose groups compared to placebo.

The following is the sample SAS code that will be used to implement this analysis:

```
PROC MIXED DATA= DATAIN;
CLASS TRT01PN STRATF;
MODEL CHG_WEEK12 = TRT01PN BASE STRATF / SOLUTION;
LSMEANS TRT01PN / CL DIFF OM;
LSESTIMATE TRT01PN "Difference at Week 12" 1 1 1 -3 / CL e OM;
LSESTIMATE TRT01PN "Combined at Week 12" 1 1 1 0 / CL e OM;
RUN;
```

Where TRT01PN = Planned Treatment Group Number; BASE = Baseline Value; CHG_WEEK12 = Change from Baseline at Week 12; STRATF = Stratification Factor.

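### Sample SAS code for two robustness analyses does not give the placebo comparisons the SAP text asks for: the pattern-mixture pooling mixes comparators, and the ANCOVA combined-dose contrasts lack a divisor of 3

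*SAP*

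**What the plan says.** **Pattern-mixture analysis (SAP 6.12.4.1).** After imputation, each dataset is analysed with the primary MMRM. The text says that LS means and "their differences between treatments will be combined across all 20 imputed datasets". The sample code for the differences first runs "PROC SORT DATA= DIFFS; BY TRT01PN; RUN" and then "PROC MIANALYZE DATA= DIFFS(WHERE=(AVISITN=_AVISITN)); MODELEFFECTS ESTIMATE; STDERR STDERR; ODS OUTPUT PARAMETERESTIMATES= DIFFS_COMB; BY TRT01PN AVISITN; RUN".

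**Where the differences come from (SAP 6.12.3).** The only printed step that creates `DIFFS` is the ODS output of "LSMEANS TRT01PN*AVISITN / CL DIFF OM" in the primary model, which sets no control level. The model lists "randomized treatment (2.5 mg, 5.0 mg, 7.5 mg, or placebo b.i.d"; the placebo coefficient of -3 sits on the fourth treatment level. Sections 6.12.2 and 6.12.3 define the differences of interest as mesdopetam against placebo. The combined-dose contrast at Week 12 ends, after the minus sign of the placebo coefficient, with "3 divisor = 3 / CL e OM".

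**ANCOVA (SAP 6.12.5.2).** The text promises "treatment difference estimates, SEs, and p-values for each dose level and combined dose groups compared to placebo". The code for the combined-dose difference is "LSESTIMATE TRT01PN 'Difference at Week 12' 1 1 1 -3 / CL e OM". A companion contrast for the combined-dose mean has coefficients `1 1 1 0`. Neither has a divisor.

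**The concern.** In the pattern-mixture code, keeping same-visit pairs removes cross-visit comparisons but leaves dose-against-dose comparisons in place. PROC MIANALYZE treats every row in a BY group as an imputation of one quantity. It would average differences against different comparators and count the spread between comparators as between-imputation variance. The estimate is then wrong and the SE is inflated. If the higher doses have a positive effect, the 2.5 mg and 5 mg effects are understated, so the stress test of the missing-at-random assumption could make them look fragile when they are not. This analysis matters here because SAP Section 4 records more dropout than expected and an increase to 154 randomized patients.

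In the ANCOVA code, `1 1 1 -3` returns the sum of three dose-placebo differences rather than their mean. The combined-dose effect would look three times the corresponding MMRM effect. Because the p-value does not change, checking p-values would not reveal it.

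**Working it through.** **Inputs.** 20 imputations (6.12.4.1); difference 3 h, SD 3.5, 31 evaluable per arm (SAP Section 4); two-sided alpha 0.05 (protocol 14.2). Assumptions: numeric treatment codes run 2.5 mg, 5 mg, 7.5 mg, placebo; 3 h applies to every dose; between-imputation variance is zero at first.

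**Scale check.** The SE of one dose-placebo difference is 3.5 × √(2/31) = 0.889. Then 3/0.889 = 3.37, and the power is 0.921 by the normal approximation (0.913 by noncentral t). This agrees with the stated 92%, so the inputs are on the plan's own scale.

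**Rows per BY group at one visit.** With all pairwise differences, each arm is paired with every later-coded arm:

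| Group | Comparators pooled | Rows |
|---|---|---|
| 2.5 mg | 5 mg, 7.5 mg, placebo | 3 × 20 = 60 |
| 5 mg | 7.5 mg, placebo | 2 × 20 = 40 |
| 7.5 mg | placebo | 20 |

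The row counts depend on no assumed effect. With placebo last, two of the three doses are affected whatever the order of the active codes.

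**What the pooled mean estimates.** Write d for the effect of each dose against placebo.

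- 2.5 mg: [(d2.5 − d5) + (d2.5 − d7.5) + d2.5]/3 = d2.5 − (d5 + d7.5)/3
- 5 mg: [(d5 − d7.5) + d5]/2 = d5 − d7.5/2

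**Rubin's rules at 3 h for every dose.** Within variance W = 2 × 3.5²/31 = 0.790; total variance T = W + (1 + 1/m)B.

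- 2.5 mg as coded: 40 rows at 0 and 20 at 3; mean 1.0; B = 120/59 = 2.034; T = 0.790 + (61/60) × 2.034 = 2.858; SE 1.69; df 113; p about 0.56.
- 5 mg as coded: 20 rows at 0 and 20 at 3; mean 1.5; B = 90/39 = 2.308; T = 0.790 + (41/40) × 2.308 = 3.156; SE 1.78; df 69; p about 0.40.
- Either dose, placebo rows only: 3.0 h, SE 0.889, t = 3.37, p about 0.001.

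**Sensitivity to the assumptions.**

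- The documents give no between-imputation SD. If it were 0.4 h, the correct SE would be √(0.790 + 1.05 × 0.16) = 0.98. The SEs as coded would be 1.74 (2.5 mg) and 1.82 (5 mg).
- With assumed effects of 1, 2 and 3 h, the code returns 1 − 5/3 = −0.67 h for 2.5 mg (correct: 1.0 h) and 2 − 1.5 = 0.50 h for 5 mg (correct: 2.0 h).

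**ANCOVA.** For `1 1 1 -3` the estimate is 3 + 3 + 3 = 9 h. SE = 3.5 × √((1 + 1 + 1 + 9)/31) = 2.178. The df are 124 − 6 = 118 (four arms, baseline, stratum), and the 95% CI is 4.69 to 13.31. Dividing by 3 gives 3.0 h, SE 0.726, CI 1.56 to 4.44. t = 4.13 both ways, so p is unchanged. Likewise `1 1 1 0` returns three times the combined-dose mean.

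**Slips that would probably stop the programs first.** `DIFFS` is sorted by `TRT01PN` only but processed by `TRT01PN AVISITN`, which is out of order once 20 datasets are stacked. Section 6.12.5.2 has LSESTIMATE where 6.12.3 has LSMESTIMATE. The MNAR statement names `TRT01P`, while CLASS declares `TRT01PN`. These are the slips a programmer would notice; the missing comparator and divisor raise no error.

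**The case against.** The SAP labels its code as sample code, and the MIANALYZE step follows its own sentence on how results are to be summarized. The MMRM run by imputation is described only in prose, so a placebo restriction in that unprinted step cannot be excluded. The numeric treatment codes are not given: placebo last follows from the contrast coefficients, but the order of the active doses is inferred from the listing. The printed programs would probably halt, and SAP 6.3.3 requires independent double programming. A validator working from the text would compare with placebo.

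The illustration is also rough. The imputed analysis would use more than 31 per arm (at 35, SE = 3.5 × √(2/35) = 0.84), and control-based imputation pulls the true value down. With 10% dropout it could be near 0.9 × 3 = 2.7 h. The separate tipping-point analysis also tests the missing-at-random assumption for any significant dose, and a 9 h combined effect beside single-dose differences near 3 h would be conspicuous.

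These points limit the consequence and make the hour and p-value figures approximate. They do not remove the error. At 2.7 h for every dose, the pooling would still return 0.9 h and 1.35 h. Nothing printed restricts the comparator or supplies the divisor, and two programmers who both start from the SAP code could reproduce the same result.

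**Conclusion.** Both errors stand on the printed code. Provided that only the halting slips are repaired and the arms are coded in the listed order, the pattern-mixture results for 2.5 mg and 5 mg are not placebo comparisons. At the planning values they would be 1.0 h and 1.5 h instead of 3.0 h, with SEs about twice the correct one. The ANCOVA combined-dose estimate, SE and CI are exactly three times too large, whatever the effect size.

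Not affected are the primary MMRM, the testing hierarchy, the single-dose ANCOVA differences and the ANCOVA p-values. The 7.5 mg pattern-mixture result is also unaffected under the listed coding; it would be affected if 7.5 mg were not the last active code. This should be corrected, but it does not put the primary conclusion at risk.

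**What to change.** - **SAP 6.12.4.1:** restrict `DIFFS` to rows with `_TRT01PN` equal to placebo, or add `_TRT01PN` to the BY list and report the placebo rows. Sort by all BY variables and check that each pooled comparison has exactly 20 rows. Use one treatment variable name in the CLASS and MNAR statements. State in the text that the pooled differences are each dose against placebo.
- **SAP 6.12.5.2:** use LSMESTIMATE with `divisor = 3` on both contrasts, as in 6.12.3.
- State the numeric treatment codes once, so that the contrasts and comparator filter can be checked against them.

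The cost is a few lines of SAP code and text, with no change to design, data collection or the primary analysis.

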6.12.4.2 Tipping Point Analysis

If the primary efficacy analysis significantly favours mesdopetam, a tipping-point sensitivity analysis for the primary efficacy endpoint will be conducted on the significant dose groups to investigate how severe the departure from the MAR assumption must be to overturn the conclusion from the primary analysis. In this analysis, the assumption will be that missing data in the active treatment groups follows a MNAR pattern.

A tipping-point approach will be used such that the trajectories of the patients in the active treatment groups after early termination from study are assumed to be worse than placebo by a fixed amount (δ). Missing values will first be imputed using a MAR approach and then the value of δ will be deducted from all imputed values occurring after early termination for patients in the active treatment groups only. The value of δ will be applied in increments of 0.5 hours (i.e., 0.5h, 1h, 1.5h, 2h) up to the point at which the treatment difference at Visit 5 (Week 12) is no longer statistically significant at the local level (see Section 0). This analysis provides a measure of the degree by which the patients in the active treatment groups who discontinued early would need to be worse, compared to patients with similar trajectories up to the point of discontinuation in the same treatment arm, at each post-discontinuation visit for the null hypothesis of no treatment difference to no longer be rejected.

6.12.4.3 Modified stratification factor

The analysis of the primary endpoint will be repeated using the modified stratification factor in the mixed model for repeated measures (MMRM) on the randomised dose group.

QMD Ref: Worldwide-TMP-ST-005-7.0 Effective: 12Aug2019	Governing QMD: Worldwide-SOP-ST-001
Confidentiality	v Statement
This document is the property of Worldwide Clinical Trials Inc. and may ne prior approval from Worldwide Quality Assurance or in compl	
REF: Worldwide-TMP-QA-001f-1.3	Page 32 of 49

Worldwide Clinical Trials Controlled Quality Management Document		
WORLDWIDE CLINICAL TRIALS	Sponsor:	Integrative Research Laboratories Sweden AB
	Protocol Number:	IRL790C005
STATISTICAL ANALYSIS PLAN. PHASE 2-3-4		

6.12.5 Supportive Analyses

6.12.5.1 Per Protocol Analysis

The per protocol analysis will follow the same analysis method as the primary analysis, with the exception that the analysis will be based on the PPS.

6.12.5.2 ANCOVA Analysis

An analysis of covariance (ANCOVA) will also be performed using the FAS. The ANCOVA model will be adjusted for the following covariates: randomized treatment, baseline value for average daily hours of ON time without troublesome dyskinesia (continuous covariate), as well as randomisation stratification factor for daily hours spent in ON-time with troublesome dyskinesia (<6 hours, \geq 6 hours). The dependent variable is the change from baseline in average daily ON-time (hours) at Week 12. Missing observations will not be imputed.

The LS means, SEs, and 95% CIs will be provided for each treatment group, as well as treatment difference estimates, SEs, and p-values for each dose level and combined dose groups compared to placebo.

The following is the sample SAS code that will be used to implement this analysis:

```
PROC MIXED DATA= DATAIN;
CLASS TRT01PN STRATF;
MODEL CHG_WEEK12 = TRT01PN BASE STRATF / SOLUTION;
LSMEANS TRT01PN / CL DIFF OM;
LSESTIMATE TRT01PN "Difference at Week 12" 1 1 1 -3 / CL e OM;
LSESTIMATE TRT01PN "Combined at Week 12" 1 1 1 0 / CL e OM;
RUN;
```

Where TRT01PN = Planned Treatment Group Number; BASE = Baseline Value; CHG_WEEK12 = Change from Baseline at Week 12; STRATF = Stratification Factor.

6.12.5.3 Impact of Permitted Dose Reduction

The impact of permitted dose reductions on the primary analysis will be explored.

The change from baseline in average daily ON-time without troublesome dyskinesia (hours) by visit will be analysed and reported (including line plots) using the same MMRM approach as for

Worldwide Clinical Trials Controlled Quality Management Document		
WORLDWIDE CLINICAL TRIALS	Sponsor:	Integrative Research Laboratories Sweden AB
	Protocol Number:	IRL790C005
STATISTICAL ANALYSIS PLAN. PHASE 2-3-4		

the primary analysis, except the adjusted dose groups will be used as the treatment factor and pooled dose will be excluded from tabulations.

LS means, SE, and 95% CI for the change from baseline by treatment group as well as the estimated treatment difference, SE, and p-value for each dose level compared to placebo, will be reported, and compared to the primary analysis at Week 12.

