	A dose reduction is only allowed if the patient experiences an increase in parkinsonism and/or a consistent increase in motor OFF-time. Increased parkinsonism is manifested as consistent increase in disability associated with parkinsonian symptoms (i.e. bradykinesia, tremor and/or rigidity).
	The following steps are permitted if the dose is decided to be reduced:
	Patients allocated to 7.5 mg b.i.d. \rightarrow dose is reduced to 5 mg b.i.d.
	Patients allocated to 5 mg b.i.d. \rightarrow dose is reduced to 2.5 mg b.i.d.
	Patients allocated to 2.5 mg b.i.d. \rightarrow dose is maintained (i.e. 2.5 mg b.i.d.).
	Patients allocated to placebo b.i.d. \rightarrow placebo b.i.d. is maintained.

Confidential	Version: 5.0	Page 40 of 74
Protocol: IRL790C005	Date: 5 Mar 2021	C

	If parkinsonism is still increased following this dose reduction, the patient and Investigator need to decide if the patient could continue with the same dose in the study (since the dose cannot be reduced further) or if the patient have to withdraw the IMP and the study. Dose reduction will be managed through the IRS system.
Patient motor function review performed at Visit 3 (Day 28 ±4 days)	This review is based on the 24-hour patient home diaries completed in the week prior to Visit 3 and the MDS-UPDRS part II assessment completed during site Visit 3. Diaries and MDS-UPDRS data are reviewed and compared to baseline.
	If there is a clinically relevant increase in OFF-time, the Investigator must determine if the increase has been consistent over time and if it is predominantly related to non-motor or motor OFF-time (according to the Investigator's clinical judgement). Evaluation of results from MDS-UPDRS part 2 (M-EDL) should be weighted in the decision. Adherence to prescribed antiparkinsonian medications should also be reviewed.
	Should a consistent increase in motor OFF-time, and/or a clinically significant worsening of mobility due to parkinsonism be assessed as likely due to the IMP, the dosing should be reduced by 2.5 mg b.i.d. at this visit. If the patient has already had a dose reduction prior to Visit 3, the dose cannot be reduced further at this visit, and the Investigator must determine whether the patient can continue in the study (i.e. continue in the study with the same dose).
	Other AEs not relating to the core symptoms of parkinsonism (such as, fatigue, headache, dystonia and other) do not qualify for dose reduction.

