6.2.16 Definition of Adjusted Dose Group

To account for patients who have a permitted dose reduction and remain stable thereafter, adjusted dose groups will be defined. Patients randomly allocated to mesdopetam and who had a permitted dose reduction of 2.5 mg recorded at Visit 3, will be counted in the treatment group one dose lower than their randomized treatment. Patients randomly allocated to placebo but who had a dose reduction will remain in the placebo group.

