6.12 Primary Efficacy Analyses

All applicable statistical tests will be performed at a local significance level consistent with an overall FWER of 5% and the multiple testing strategy described in Section 0. All comparisons between treatments will be reported with 95% confidence intervals (CI) for the difference. All efficacy analyses will be performed by randomized treatment group and adjusted dose group for patients in the FAS, as well as all active doses grouped compared to placebo.

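### The adjusted-dose analysis moves patients who worsened into the next lower dose group and tests against an unselected placebo arm, so supportive p-values can suggest a dose-response that is not there.

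*SAP*

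**What the plan says.** Protocol 9.2, Table 3, sets the trigger: "A dose reduction is only allowed if the patient experiences an increase in parkinsonism and/or a consistent increase in motor OFF-time". The decision can be taken from Visit 2 (Day 9) until Visit 3 (Day 28 ± 4 days). Of the motor review at Visit 3 the table says: "This review is based on the 24-hour patient home diaries completed in the week prior to Visit 3". The review also uses the MDS-UPDRS part 2 rating from that visit. A 7.5 mg patient steps to 5 mg and a 5 mg patient to 2.5 mg. Patients on 2.5 mg or placebo keep what they have.

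SAP 6.2.16 turns this into analysis groups. Reduced mesdopetam patients "will be counted in the treatment group one dose lower than their randomized treatment". For the control arm: "Patients randomly allocated to placebo but who had a dose reduction will remain in the placebo group".

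SAP 6.12.5.3, under the heading of supportive analyses, repeats the primary MMRM, "except the adjusted dose groups will be used as the treatment factor", and reports the "estimated treatment difference, SE, and p-value for each dose level compared to placebo". The results are then compared with the primary analysis at Week 12. No caveat about selection is given.

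On reach, SAP 6.12 states: "All efficacy analyses will be performed by randomized treatment group and adjusted dose group for patients in the FAS". SAP 6.1.2 says instead that efficacy is presented by randomised treatment in the FAS.

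**The concern.** Membership of an adjusted dose group depends on something that happens after randomisation and is related to the outcome. OFF-time and ON-time without troublesome dyskinesia are competing entries in the same 24-hour diary, and the Visit 3 review reads the diaries that supply the Week 4 value of the model. The 7.5 mg group loses patients who worsened. The 2.5 mg group keeps its own and gains those from 5 mg. Placebo keeps all of its own.

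The resulting order, with 7.5 mg best and 2.5 mg worst, is the one the sponsor expects: SAP 6.15 states the hypothesis that 7.5 mg is the most efficacious dose. Dose-response is a secondary objective. A table with p-values against placebo that shows this order could be read as support for it when it reflects only how the groups were formed.

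**Working it through.** **The plan's own figure.** SAP section 4 gives a 3 h difference, SD 3.5 h, 31 evaluable per arm and 92% power; Protocol 14.2 gives two-sided 0.05. The standard error is 3.5 × √(2/31) = 0.889 h, and 3/0.889 = 3.375. Power is Φ(3.375 − 1.960) = Φ(1.415) = 0.921. Also 31/0.90 = 34.4, so 35 per arm and 140 in all. The figure reproduces, and the same SD and n are used below.

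**Assumptions the documents do not supply.** q is the proportion reduced, taken as equal in all arms because there is no drug effect. r is the correlation between the worsening that triggers reduction and the Week 12 change. A 2.5 mg patient with a recorded reduction is taken to stay at 2.5 mg, since Table 3 maintains that dose.

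**Bias in closed form.** Let the worst fraction q on a normal trigger be reduced, and let φ be the normal density at the cut-off. Reduced patients then have a mean Week 12 change of −r·SD·φ/q relative to their arm. Moving them gives, against placebo:
- 7.5 mg: +r·SD·φ/(1 − q)
- 5 mg: 0, because it loses and gains equal numbers with the same mean
- 2.5 mg: −r·SD·φ/(1 + q)

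Example with q = 20%, r = 0.5 and φ = 0.280: r·SD·φ = 0.5 × 3.5 × 0.280 = 0.49 h. The bias is +0.49/0.80 = +0.61 h at 7.5 mg and −0.49/1.20 = −0.41 h at 2.5 mg. The false gap between the two doses is 1.02 h, about the 1 h shift that Protocol 11.2.3.1 treats as clinically meaningful.

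**Type I error.** This comes from simulated null trials with 31 per arm. Groups were formed by the SAP 6.2.16 rule and the Week 12 contrast used the variance pooled over four groups, which is close to the unstructured MMRM with complete data and no covariates.

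| q | r | 7.5 mg bias (h) | 2.5 mg bias (h) | Two-sided error, 7.5 mg vs placebo |
|---|---|---|---|---|
| 5% | 0.3 | +0.11 | −0.10 | about 5% |
| 10% | 0.25 | +0.17 | −0.14 | 5 to 5.5% |
| 10% | 0.5 | +0.34 | −0.28 | about 6% |
| 20% | 0.25 | +0.31 | −0.20 | 6 to 6.5% |
| 20% | 0.5 | +0.61 | −0.41 | 9 to 10% |
| 20% | 0.7 | +0.86 | −0.57 | about 14% |

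Simulated biases agree with the closed form to within about 0.03 h. At q = 20% and r = 0.5 nearly all false positives favour the drug: about 9% of trials, against 2.5% nominal. With r = 0 there is no bias. With the same data grouped by randomised dose, the bias is about zero and the error returns to about 5%.

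**The case against.** **This is supportive output, and the protocol asked for something like it.** Both parts are true. Protocol 14.9.2 announces an analysis by treatment received after Visit 3, so producing one is not an SAP error. A reader might infer that the trial's type I error or its formal dose-response conclusion is compromised. The documents do not support that. The primary model (SAP 6.12.3) uses randomised treatment, the gatekeeping in 6.15 has no adjusted-dose step, and the dose-response step in 6.13.3.4 starts from the primary model.

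**The sentence in SAP 6.12 need not reach every endpoint.** A reader might infer that all efficacy inference will also be run on adjusted groups. The sentence permits that reading, but it stands under the primary-analysis heading, 6.1.2 says randomised treatment, and 6.13 and 6.14 list dose levels without naming adjusted groups. What stands is an inconsistency to resolve.

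**The trigger is not simply the Week 4 diary result.** Reductions can occur from Day 9, before the Visit 3 diaries exist. The Visit 3 review also weighs MDS-UPDRS part 2, consistency over time, motor versus non-motor OFF-time, medication adherence and attribution to study drug. This lowers r and is why the table includes small values. It does not make r zero.

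**The reduction rate is unknown.** In phase 2a (Protocol 4.6), 9 of 39 mesdopetam patients (23%) reported parkinsonism during titration only. They were on active drug titrated until signs of intolerability, so this does not fix a rate for a no-effect scenario.

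**Leaving Week 4 out of this model** might look like a remedy. It is not one: the Week 12 bias comes from the regrouping and would remain.

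**Conclusion.** The point holds for the supportive adjusted-dose analysis. Its direction follows from the SAP's own grouping rule whenever the reduction trigger is related to the Week 12 outcome. Under no drug effect and equal reduction rates, 7.5 mg is favoured, 2.5 mg is penalised and 5 mg is about neutral; it would be wrong to say that every lower dose is biased. If rates differ by dose, the neutrality of 5 mg no longer holds.

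The size depends on two unknowns. It is negligible if few patients are reduced and the trigger is weakly related to the outcome. It comes close to the 1 h yardstick at 7.5 mg only with about 20% reduced and a strong relation. What is at stake is a misreading of supportive tables and plots as evidence of dose-response, not the validity of the primary result.

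**What to change.** - In SAP 6.12.5.3, keep the adjusted-dose estimates and plots as description and remove the p-values against placebo.
- Add a sentence there, and as a footnote to the outputs, that the groups are not randomised, that active patients are regrouped after motor worsening, and that placebo patients are not.
- Reconcile SAP 6.12 with 6.1.2, and state that efficacy and dose-response inference is by randomised dose only.

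Week 4 can stay in the model. The cost is SAP wording and the loss of p-values from supportive tables. Dosing, data collection, the primary analysis and the multiplicity procedure do not change.
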